## 7. ANALYSIS INTERPRETATION

Comparative analyses will be descriptive with the aim to characterize the difference in reactogenicity/immunogenicity between groups.

With respect to the secondary objective and decision rule linked to the use of an adjuvant, the interpretation will be done according to the CI for the ELISA anti-stalk group GMT ratios (pooled AS01 vs pooled non-adjuvanted and pooled AS03 vs pooled non-adjuvanted) as measured 28 days after the last planned priming dose. The use of the adjuvant (AS01 or AS03) will be considered justified if the lower limit of the 94.46% CI of the group GMT ratio (adjuvanted vs non adjuvanted) is >1.50.

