## 2. STUDY DESIGN

\*If a subject presents signs and symptoms of influenza-like illness (ILI), nasal and throat swabs will be collected as soon as possible (preferably within 24 hours, but not later than 7 days) after the onset of an ILI to test for influenza and/or other respiratory pathogens by RT-PCR **if deemed necessary or for storage**.

\*\*IDMC reviews will be performed throughout the study.

- **Experimental design:** Phase I/II, observer-blind, randomized, controlled, multi-centric study with 10 parallel groups.
- **Study groups:**
  - **cH8/P/cH5-AS03 group:** 47 subjects receiving one dose of cH8/1N1+AS03 at Day 1, one dose of PBS at Day 57 and one booster dose of cH5/1N1+AS03 at Month 14.
  - **cH5/P/cH8-AS03 group:** 47 subjects receiving one dose of cH5/1N1+AS03 at Day 1, one dose of PBS at Day 57 and one booster dose of cH8/1N1+AS03 at Month 14.
  - **cH8/5/11-AS03 group:** 47 subjects receiving one dose of cH8/1N1+AS03 at Day 1, one dose cH5/1N1+AS03 at Day 57 and one booster dose of cH11/1N1+AS03 at Month 14.
  - **cH8/P/cH5-AS01 group:** 47 subjects receiving one dose of cH8/1N1+AS01 at Day 1, one dose of PBS at Day 57 and one booster dose of cH5/1N1+AS01 at Month 14.
  - **cH5/P/cH8-AS01 group:** 47 subjects receiving one dose of cH5/1N1+AS01 at Day 1, one dose of PBS at Day 57 and one booster dose of cH8/1N1+AS01 at Month 14.
  - **cH8/5/11-AS01 group:** 47 subjects receiving one dose of cH8/1N1+AS01 at Day 1, one dose cH5/1N1+AS01 at Day 57 and one booster dose of cH11/1N1+AS01 at Month 14.
  - **cH8/P/cH5 group:** 47 subjects receiving one dose of cH8/1N1 at Day 1, one dose of PBS at Day 57 and one booster dose of cH5/1N1 at Month 14.
  - **cH5/P/cH8 group:** 47 subjects receiving one dose of cH5/1N1 at Day 1, one dose of PBS at Day 57 and one booster dose of cH8/1N1 at Month 14.
  - **cH8/5/11 group:** 47 subjects receiving one dose of cH8/1N1 at Day 1, one dose cH5/1N1 at Day 57 and one booster dose of cH11/1N1 at Month 14.
  - **IIV4 group:** 47 subjects receiving one dose of *Fluarix Quadrivalent* at Day 1, one dose of PBS at Day 57 and one dose of *Fluarix Quadrivalent* at Month 14.
- **Treatment allocation:** randomized (1:1:1:1:1:1:1:1:1 ratio) using GSK Biologicals' Randomization System on Internet (SBIR). The randomization algorithm will use a minimization procedure accounting for center, sex, age (18-30 years vs. 31-39 years) and history of influenza vaccination since the 2014/2015 season (yes vs. no).

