### 6.2.3. Between group assessment

#### 6.2.3.1. ANCOVA modelling

The anti H1 HA stalk ELISA titers will be modelled using an ANCOVA model. Twenty-eight days post priming/post booster  $\log_{10}$ (titers) will be modelled as a function of the adjuvant (AS01, AS03, no adjuvant) and of the priming sequence (cH8/1N1, cH5/1N1, cH8/1N1 and cH5/1N1), including the pre-vaccination titer as covariate. The primary analysis will not include any interaction term.

For the parameter related to the priming sequence, in absence of a reference group, the overall test of difference (to reject the null hypothesis of no difference) will be done at significance level 0.10. If the test is statistically significant at level 0.10, the different pairwise comparisons will be performed at the same alpha level.

For the parameter related to the adjuvant, the pairwise comparisons to the non-adjuvant reference group (AS01 vs no adjuvant and AS03 vs no adjuvant) are planned to be performed without preamble\*. Therefore, a Dunnett test will be used for the pairwise comparisons.

\* The pairwise comparisons for the adjuvant effect will both be performed without any preliminary step (e.g. hierarchical testing) being involved. Multiplicity is being accounted for through the use of the Dunnett test.

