**Template 36 ANCOVA model for <Antibody> concentration 28 days post-priming dose(s) <cohort name>**

Source	DF (numerator)	DF (denominator)	F value	p-value
Priming sequence				
Adjuvant				

Priming sequence= different types of priming sequence - <number of modalities> modalities (<each modality>)

Adjuvant = different types of Adjuvant - <number of modalities> modalities (<each modality>)

ANCOVA model on the log-transformed concentration with the pre-vaccination log-transformed concentration as regressor, priming sequence content and Adjuvant as fixed effects

DF = degrees of freedom

Main factors (Priming sequence, Adjuvant) considered as statistically significant if p-value <0.100 (model excluding interaction)

**Template 37 Dunnett's t test for the comparison of each adjuvant against the control in terms of <Antibody> concentration 28 days post-priming dose(s) <cohort name>**

Comparison	GMC ratio	p-value	94.46% CI*	
			Lower limit	Upper limit
AS01-Non adjuvanted				
AS03-Non adjuvanted				

AS01= Pooling of results at Day 29 of ch8/P/ch5-AS01, Day 29 of ch5/P/ch8-AS01 and Day 85 of ch8/5/11-AS01

AS03= Pooling of results at Day 29 of ch8/P/ch5-AS03, Day 29 of ch5/P/ch8-AS03 and Day 85 of ch8/5/11-AS03

Non adjuvanted= Pooling of results at Day 29 of ch8/P/ch5, Day 29 of ch5/P/ch8 and Day 85 of ch8/5/11

\*Comparison performed using a 2-sided alpha=0.1 and Dunnett adjustment for multiple comparisons, resulting in an adjusted alpha=0.0554

The use of the adjuvant (AS01 or AS03) is considered justified if the lower limit of the 94.46% CI of the GMC ratio (adjuvanted versus non adjuvanted) is > 1.50

**Template 38 Pairwise comparisons of priming sequences in terms of <Antibody> concentration 28 days post-priming dose(s) <cohort name>**

Comparison	GMC ratio	p-value	90% CI	
			Lower limit	Upper limit
1 priming dose (cH8/1N1)-1priming dose (cH5/1N1)				
1 priming dose (cH8/1N1)-2priming doses (cH8/1N1 and cH5/1N1)				
1 priming dose (cH5/1N1)-2priming doses (cH8/1N1 and cH5/1N1)				

1 priming dose (cH8/1N1) = Pooling of results at Day 29 of cH8/P/cH5-AS01, Day 29 of cH8/P/cH5-AS03 and Day 29 of cH8/P/cH5

1 priming dose (cH5/1N1) = Pooling of results at Day 29 of cH5/P/cH8-AS01, Day 29 of cH5/P/cH8-AS03 and Day 29 of cH5/P/cH8

2 priming doses (cH8/1N1 and cH5/1N1) = Pooling of results at Day 85 of cH5/11-AS01, Day 85 of cH8/5/11-AS03 and Day 85 of cH8/5/11

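### The adjuvant rule is valid, but a step-down Dunnett version would give the second adjuvant up to about 11 points more power at the same familywise error

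*SAP*

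**What the plan says.** Section 6.2.3.1 models log10 anti-H1 stalk ELISA titers on adjuvant, priming sequence and baseline titer, and compares AS01 and AS03 each with no adjuvant. On multiplicity it says: "Therefore, a Dunnett test will be used for the pairwise comparisons". A footnote adds that the two comparisons "will both be performed without any preliminary step (e.g. hierarchical testing) being involved" and that "Multiplicity is being accounted for through the use of the Dunnett test".

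Section 7 turns the result into a decision: use of either adjuvant is "considered justified if the lower limit of the 94.46% CI of the group GMT ratio (adjuvanted vs non adjuvanted) is >1.50". Template 37 in Annex 2 repeats this and gives the origin of the level: "Comparison performed using a 2-sided alpha=0.1 and Dunnett adjustment for multiple comparisons, resulting in an adjusted alpha=0.0554". One interval level is shown for both adjuvants, whatever the other shows.

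For priming sequence, the same section 6.2.3.1 plans an overall test at 0.10 and, if that is significant, pairwise comparisons at 0.10. Template 38 shows these with 90% intervals.

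**The concern.** With two null hypotheses, the Dunnett level is needed only while both could be true. Once one adjuvant has been shown to exceed 1.50, a single hypothesis remains, and it can be tested at the unadjusted level without raising the familywise error. The SAP keeps the wider interval for the second adjuvant anyway. On the log scale its half-width is 1.916/1.645 = 1.165 times that of the 90% interval.

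At stake is the verdict on the second adjuvant. When one adjuvant clearly works, the other is more often declared not justified than the familywise error rate requires.

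**Working it through.** **Inputs**
- Two-sided familywise alpha 0.10 and adjusted alpha 0.0554: Template 37.
- Margin 1.50: section 7.
- Two comparisons sharing one reference pool: section 6.2.3.1. With equal pools their correlation is 0.5.
- 47 subjects per group: section 2. Template 37 pools three groups per adjuvant level, for example "AS01= Pooling of results at Day 29 of ch8/P/ch5-AS01, Day 29 of ch5/P/ch8-AS01 and Day 85 of ch8/5/11-AS01". So 3 × 47 = 141 per pool and 9 × 47 = 423 in the model.
- Six parameters (intercept, 2 adjuvant, 2 priming sequence, 1 baseline), so 423 − 6 = 417 error degrees of freedom.
- SD, expected ratio and power: not in the SAP. A residual SD of 0.3 to 0.6 on the log10 scale is assumed below. Dropout is ignored.

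**1. The plan's own figure.** For k = 2, correlation 0.5, two-sided 0.10 and 417 df, the Dunnett critical value is 1.921 and the per-comparison alpha is 0.0554. This matches the SAP. The normal approximation, used from here on, gives 1.916.

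**2. The step-down rule and its error.** Let T be each log ratio minus log 1.50, divided by its standard error. The larger T is compared with 1.916. If it passes, the other is compared with 1.645. If it fails, neither adjuvant passes.
- Both true ratios at 1.50: any false pass needs the larger T above 1.916. The probability is 5.0%, as under the current rule.
- One adjuvant clearly effective, the other at 1.50: the false-pass probability for the second is 0.0554/2 = 2.8% under the current rule and 5.0% under step-down, which is the familywise limit.
- A T above 1.916 passes under both rules, so no pass is reversed.

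**3. Power for the second adjuvant when the first is certain to pass.** If single-step power is p, step-down power is Φ(z_p + 1.916 − 1.645) = Φ(z_p + 0.271).

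| Single-step | Step-down | Gain (points) |
|---|---|---|
| 50% | 60.7% | 10.7 |
| 80% | 86.7% | 6.7 |
| 90% | 94.0% | 4.0 |
| 95% | 97.2% | 2.2 |
| 99% | 99.5% | 0.5 |

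The maximum gain is 10.8 points, at single-step power of about 45%.

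**4. Equal true effects (bivariate normal, correlation 0.5).** The unconditional gain per adjuvant is 5.0, 4.4, 3.0 and 1.8 points at single-step power of 50, 80, 90 and 95%. Given that the other has passed, it is 10.0, 5.5, 3.3 and 1.9 points. Power to justify both goes from 56% to 66%, 69% to 78% and 83% to 89% at single-step power of 70, 80 and 90%.

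**5. On the ratio scale, under assumed SDs.** The observed ratio needed is 1.5 × 10^(c × SD × √(2/141)), with c = 1.916 or 1.645. For SD 0.5 the exponents are 0.114 and 0.098, giving 1.95 and 1.88.

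| SD (log10) | Needed now | Needed by the second under step-down |
|---|---|---|
| 0.3 | 1.76 | 1.72 |
| 0.4 | 1.85 | 1.80 |
| 0.5 | 1.95 | 1.88 |
| 0.6 | 2.06 | 1.97 |

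Power for the second adjuvant, with the first certain to pass: SD 0.4 and true ratio 2.0 gives 76.0% against 83.6%; SD 0.5 and ratio 2.5 gives 96.5% against 98.1%; SD 0.3 and ratio 2.25 gains 0.1 point. Over SD 0.3 to 0.6 and ratios 1.6 to 3, the gain runs from 0 to 10.8 points.

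**The case against.** The strongest reply is that nothing here is wrong. The level is correct, the familywise error is held, and the choice was deliberate. All of that stands.

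It can also be said that step-down conflicts with the footnote excluding a preliminary step. Read in context, the footnote excludes a gate before the comparisons. Step-down adds none and fixes no order: either adjuvant can pass first, at exactly the present limit. It does make the second verdict depend on the first.

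A reader might infer that the current rule gives up power for no return. It does not. One interval serves as both simultaneous estimate and decision limit. Under step-down, the second adjuvant could be called justified while its 94.46% interval includes 1.50, and its error at a true ratio of exactly 1.50 rises from 2.8% to 5% when the other is clearly effective. The SAP does already accept unadjusted 90% intervals after a 0.10 overall test for priming sequence, so this structure is not foreign to it.

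Timing is a fair objection too. The rule is the same in all four SAP versions. Its data feed the Day 85 interim analysis, for which the sponsor's statistician is unblinded (section 8.1), and Amendment 3 is dated 12 September 2019. The SAP does not say when that interim ran.

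**Conclusion.** The rule is valid but less efficient than it could be. Step-down Dunnett recovers at most about 11 points for the second adjuvant when the other passes, about 2 to 5 points per adjuvant unconditionally with equal effects at single-step power of 50 to 95%, and almost nothing at very high power. These figures rest on equal pools, correlation 0.5 and normal critical values. Without an SD or expected ratio in the SAP, the gain in this trial cannot be stated.

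Two stronger readings are not supported. One is that the second adjuvant is judged at half the planned error rate: 0.10 is the familywise rate, 0.0554 is the plan's own per-comparison rate, and 0.0554/0.10 is 55%. The other is that this is the only formal decision in the SAP: section 6.2.3.1 also tests priming sequence, and Templates 39 and 40 provide for success-criteria tables.

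This is an optional, cheap improvement.

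**What to change.** In sections 6.2.3.1 and 7 and in Template 37, state a step-down Dunnett rule:
- The adjuvant with the larger test statistic against 1.50 is justified if its 94.46% lower limit exceeds 1.50.
- If it passes, the other is justified if its 90% lower limit exceeds 1.50.
- If the first fails, neither is justified.

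Keep reporting the 94.46% intervals for both as the simultaneous intervals, and note that the second decision may differ from what its 94.46% interval alone would show.

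The cost is a few sentences and one extra interval column, with no new data or model. The change must be fixed before the Day 29 and Day 85 results are unblinded. If they have already been unblinded, keep the current rule as the decision and present the step-down result as a labelled supplementary analysis.

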## 8. CONDUCT OF ANALYSES

Any deviation(s) or change(s) from the original statistical plan outlined in this statistical analysis plan will be described and justified in the final Study Report.

### 8.1. Sequence of analyses

All interim analyses will be conducted on data as clean as possible. The final analysis will be performed on fully clean data.

Excluding the IDMC monitoring analyses, the analyses will be performed in a stepwise manner:

- Three interim analyses will be performed:
  - When safety, reactogenicity and immunogenicity (including at least H1 anti-stalk ELISA) data from all subjects are available up to Day 85 (Visit 6).

- When immunogenicity (including at least H1 anti-stalk ELISA) data are available from Phase I subjects eligible for booster vaccination who have completed their Visit 10 according to the allowed interval.
- When safety, reactogenicity and immunogenicity (including at least H1 anti-stalk ELISA) data from all subjects are available up to Month 14 + 28 days.
- The GSK statistician/statistical analyst will be unblinded for these analyses (i.e. will have access to the individual subject treatment assignment). The remaining GSK study personnel will remain blinded (see Section 5.3 of the protocol).
- A final analysis of all data will be performed when all data up to study conclusion are available. This analysis will be reported in an integrated Study Report and made available to the investigators.

If the data for tertiary endpoints become available at a later stage, (an) additional analysis/analyses will be performed. These data will be documented in annex(es) to the Study Report and will be made available to the investigators at that time.

Description	Analysis ID	Disclosure Purpose (CTRS = public posting, SR = study report, internal)	Dry run review needed (Y/N)	Study Headline Summary (SHS) requiring expedited communication to upper management (Yes/No)	Reference for TFL
Final analysis	E01_01	SR, CTRS	Y	Yes	See columns R, S, T, U in TFL TOC
Interim analysis at Day 85	E01_02	Internal	Y	Yes	See columns R, S, T, U in TFL TOC
Interim analysis at Month 14 + 28 days when Phase I subjects completed Visit 10	E01_25	Internal	Y	Yes	See columns R, S, T, U in TFL TOC
Interim analysis at Month 14 + 28 days	E01_03	Internal	Y	Yes	See columns R, S, T, U in TFL TOC

## 8.2. Statistical considerations for interim analyses

No statistical adjustment will be made for the interim analyses, which are intended to provide final outputs related to the different endpoints and timepoints in a phased manner.

## 9. CHANGES FROM PLANNED ANALYSES

Not applicable.

## 10. NON-STANDARD DATA DERIVATION RULES AND STATISTICAL METHODS

Not applicable (covered in Section 12).

## 11. LIST OF FINAL REPORT TABLES, LISTINGS AND FIGURES

The TFL TOC provides the list of tables/listings and figures needed for the study report. It also identifies the tables eligible for each analysis and their role (synopsis, in-text, post-text, SHS, CTRS, ...). Note that all TFL aimed to be included as post-text are noted as post-text even if these are tabulation of individual data such as listing of SAE. The post-text material contains all source material for the study report and accordingly a post-text table may be redundant with an in-text table.

The following group names will be used in the TFLs, to be in line with the T-domains:

Group order in tables	Group label in tables	Group definition for footnote
P P	cH8/P/cH5-AS03	cH8/1N1+AS03 at Day 1, PBS at Day 57, cH5/1N1+AS03 at Month 14
P P	cH5/P/cH8-AS03	cH5/1N1+AS03 at Day 1, PBS at Day 57, cH8/1N1+AS03 at Month 14
P P	cH8/5/11-AS03	cH8/1N1+AS03 at Day 1, cH5/1N1+AS03 at Day 57, cH11/1N1 + AS03 at Month 14
P P	cH8/P/cH5-AS01	cH8/1N1+AS01 at Day 1, PBS at Day 57, cH5/1N1+AS01 at Month 14
P P	cH5/P/cH8-AS01	cH5/1N1+AS01 at Day 1, PBS at Day 57, cH8/1N1+AS01 at Month 14
P P	cH8/5/11-AS01	cH8/1N1+AS01 at Day 1, cH5/1N1+AS01 at Day 57, cH11/1N1 + AS01 at Month 14
P P	cH8/P/cH5	cH8/1N1 at Day 1, PBS at Day 57, cH5/1N1 at Month 14
P P	cH5/P/cH8	cH5/1N1 at Day 1, PBS at Day 57, cH8/1N1 at Month 14
P P	cH8/5/11	cH8/1N1 at Day 1, cH5/1N1 at Day 57, cH11/1N1 at Month 14
P P	IIV4	Fluarix Quadrivalent at Day 1, PBS at Day 57, Fluarix Quadrivalent at Month 14

When all groups cannot be fit in one table, the preference is to have the investigational groups split into groups of 3 and if possible, the IIV4 control repeated on each page:

- *AS03 groups and IIV4 (cH8/P/cH5-AS03, cH5/P/cH8-AS03, cH8/5/11-AS03, IIV4)*
- *AS01 groups and IIV4 (cH8/P/cH5-AS01, cH5/P/cH8-AS01, cH8/5/11-AS01, IIV4)*
- *Non-adjuvanted groups and IIV4 (cH8/P/cH5, cH5/P/cH8, cH8/5/11, IIV4)*

## 12. ANNEX 1 STANDARD DATA DERIVATION RULE AND STATISTICAL METHODS

### 12.1. Statistical Method References

The exact two-sided 95% CIs for a proportion within a group will be the Clopper-Pearson exact CI [Clopper CJ, Pearson ES. The use of confidence or fiducial limits illustrated in the case of binomial. *Biometrika*. 1934; 26: 404-413].

The standardized asymptotic two-sided 95% CI for the group difference in proportions is based on the method described in the following paper: Robert G. Newcombe, interval estimation for the difference between independent proportions: comparison of eleven methods, *Statist Med*. 1998; 17, 873-890]. The standardized asymptotic method used is the method six.

The 95% CIs of the group GMT ratios will be computed using an ANCOVA model on the logarithm10 transformation of the titers. The ANCOVA model will include the vaccine group as fixed effects and the logarithm10 transformation of titers at Day 1. For the evaluation of adjuvant of preferred priming sequence, the vaccine group will be replaced by 2 fixed effects: the adjuvant type (AS01, AS03, No adjuvant) and the number of priming doses (1 priming dose with cH8/1N1, 1 priming dose with cH5/1N1, 2 priming doses with cH8/1N1 and cH5/1N1).

The 95% CI for GMTs will be obtained within each group separately. The 95% CI for the mean of log-transformed titer will be first obtained assuming that log-transformed values were normally distributed with unknown variance. The 95% CI for the GMTs will then be obtained by exponential-transformation of the 95% CI for the mean of log-transformed titer.

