#### 6.2.3.2. Descriptive assessment

GMT ratios and their 2-sided 95% CI will be computed after fitting an ANCOVA model on the  $\log_{10}$  transformation of ELISA/MN titers, including vaccine group as fixed effect and the pre-vaccination titer as covariate.

Differences in percentage of subjects with a fold increase from baseline and their 95% CIs will be calculated.

Generally speaking, the 4 weeks post-dose results will be compared.

The following group ratios/differences will be provided:

- Evaluation of the proof of principle:
  - cH8/5/11-AS03 vs IIV4.
  - cH8/5/11-AS01 vs IIV4.
  - cH8/5/11 vs IIV4.
- Evaluation of the number of priming doses:
  - cH8/5/11-AS03 vs cH8/P/cH5-AS03.
  - cH8/5/11-AS01 vs cH8/P/cH5-AS01.
  - cH8/5/11 vs cH8/P/cH5

- Assessment of the adjuvant systems:
  - cH8/5/11-AS03 vs cH8/5/11-AS01.
  - cH8/P/cH5-AS03 vs cH8/P/cH5-AS01.
  - cH5/P/cH8-AS03 vs cH5/P/cH8-AS01.
- Description of the priming sequence:
  - cH8/P/cH5-AS03 vs cH5/P/cH8-AS03.
  - cH8/P/cH5-AS01 vs cH5/P/cH8-AS01.

Additional ratios/differences might be considered if deemed necessary at the time analysis.

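### The ANCOVA models leave out the four minimisation factors, so intervals and tests are conservative if those factors predict the titre beyond the Day 1 value

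*SAP*

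**What the plan says.** On allocation, SAP section 2 states: "The randomization algorithm will use a minimization procedure accounting for center, sex, age (18-30 years vs. 31-39 years) and history of influenza vaccination". The history factor is a yes/no for vaccination since the 2014/2015 season.

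The current SAP describes the ANCOVA in four places, and none contains a minimisation factor:

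- Section 6.2.3.1, the two-factor model (adjuvant, priming sequence): "including the pre-vaccination titer as covariate. The primary analysis will not include any interaction term".
- Section 6.2.3.2, the GMT-ratio model: "including vaccine group as fixed effect and the pre-vaccination titer as covariate".
- Section 12.1, the method annex: "The ANCOVA model will include the vaccine group as fixed effects and the logarithm10 transformation of titers at Day 1".
- Template 36, the mock table: "ANCOVA model on the log-transformed concentration with the pre-vaccination log-transformed concentration as regressor, priming sequence content and Adjuvant as fixed effects".

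Templates 39 and 41 speak of means adjusted for covariates but name no further covariate. The SAP gives no reason for leaving the factors out, and plans neither a sensitivity analysis that includes them nor a re-randomisation test.

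The two-factor model feeds a pass/fail rule. Under section 7, an adjuvant counts as justified if the lower limit of the 94.46% CI for the pooled GMT ratio exceeds 1.50. Template 37 derives that level from a two-sided alpha of 0.1 with Dunnett adjustment, giving 0.0554 per comparison.

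**The concern.** Minimisation makes the groups more alike on the balancing factors than chance would. If a factor is prognostic, this removes its contribution to the true variance of a group difference. A model without the factor leaves that contribution in the residual and reports a standard error as if allocation had been unrestricted. The interval is then wider than the design warrants.

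What is at stake is precision and power. The sponsor set the confidence level for the adjuvant rule to four significant figures, but the interval has that coverage only if the factors add nothing to the Day 1 titre. Otherwise the 1.50 bar is harder to clear than intended, and the overall priming-sequence test that opens the pairwise comparisons is less likely to reach 0.10.

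**Working it through.** **Inputs from the SAP.** There are 47 subjects per group (section 2) and three groups per adjuvant level, so 3 × 47 = 141 per level and 9 × 47 = 423 in the two-factor model. That model has 6 parameters (intercept, 2 adjuvant, 2 sequence, 1 baseline), leaving 423 − 6 = 417 df.

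**Assumed, not in the SAP.** R² is the share of residual variance, after the Day 1 titre, that the four factors explain; it is taken as 0 to 0.20. The simulation also assumes 10 centres, factor levels equally likely, and the minimising group favoured with probability 0.8.

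**The plan's own figure.** The two-sided Dunnett critical value for two comparisons with correlation 0.5, familywise alpha 0.10 and 417 df is 1.921. The per-comparison alpha is 2 × (1 − T₄₁₇(1.921)) = 0.05537, which rounds to 0.0554, so the 94.46% level is reproduced.

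**Formulas under close balance.**

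- Width of the SAP interval relative to the adjusted one: 1/√(1 − R²).
- True level of an adjuvant comparison: 2 × (1 − Φ(z/√(1 − R²))), with z the normal quantile for 0.0554.
- True level of the overall priming-sequence test (three levels, 2 df, large-sample): exp(−2.3026/(1 − R²)), since −ln 0.10 = 2.3026.

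| R² | Width ratio | Adjuvant comparison, nominal 0.0554 | Overall sequence test, nominal 0.10 |
|---|---|---|---|
| 0 | 1.000 | 0.0554 | 0.100 |
| 0.05 | 1.026 | 0.0494 | 0.089 |
| 0.10 | 1.054 | 0.0435 | 0.077 |
| 0.20 | 1.118 | 0.0322 | 0.056 |

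**Check by simulation.** 470 subjects were minimised to 10 groups and the two-factor model was fitted with and without the four factors, 6000 runs per row. Units are residual SD = 1.

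| R² | Width ratio | SAP model: reported SE / true SD | Adjusted model: reported SE / true SD | Level, SAP model | Level, adjusted model |
|---|---|---|---|---|---|
| 0 | 0.998 | 0.1191 / 0.1195 | 0.1193 / 0.1198 | 0.058 | 0.059 |
| 0.05 | 1.025 | 0.1192 / 0.1167 | 0.1163 / 0.1166 | 0.047 | 0.054 |
| 0.10 | 1.053 | 0.1193 / 0.1135 | 0.1133 / 0.1132 | 0.042 | 0.053 |
| 0.20 | 1.118 | 0.1193 / 0.1080 | 0.1068 / 0.1074 | 0.034 | 0.057 |

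Simulation error on the levels is about √(0.0554 × 0.9446/6000) = 0.003. The SAP model's reported SE stays at 0.119 while the true SD falls as R² rises; with the factors included the two agree. With unrestricted random allocation and R² = 0.20 (1500 runs), the SAP model's reported SE (0.1191) matched the true SD (0.1196), so the mismatch comes from the minimisation.

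**Effect on the 1.50 rule.** Assume a residual SD of 0.3 to 0.6 log10, which the SAP does not give. The smallest observed ratio that passes is 1.50 × 10^(1.921 × SD × √(2/141)). This is 1.76 at SD 0.3 and 2.06 at SD 0.6. Multiplying the SD by √(1 − 0.20) gives 1.73 and 1.99.

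**Degrees of freedom.** Losing about 12 df (3 for sex, age and history, 9 for ten centres) leaves 405. The critical value is then 1.9215 and the adjusted alpha is still 0.0554.

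**The case against.** The best counter-argument is that the loss is conditional and may be small. The Day 1 titre is already in the model and may carry part of the vaccination-history effect, and age is a two-class split within 18 to 39 years. At R² = 0 nothing is lost, and nothing in the SAP supports 0.20. The error is also on the safe side, and section 7 calls the comparisons descriptive apart from a rule tied to a secondary objective. All of this stands and limits the size of the point. It does not explain why factors important enough to balance on are left out of every model.

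Two further objections also stand. The primary analysis uses a per-protocol set that varies by timepoint (sections 5.1.4 and 6.2.1), and exclusions loosen the balance that the formulas assume. Timing matters too: the same model appears in all four SAP versions since January 2018, the current one is dated September 2019, and section 8.1 plans a Day 85 analysis that unblinds the sponsor's statistician. The SAP does not say whether that analysis had been run. Changing the decision model after it could look data-driven.

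A reader might infer that the intervals are certainly too wide, or that the adjuvant rule is invalid. The document supports neither: the residual R² is not given, the estimates are unbiased and the type I error is not inflated. A reader might also apply a one-df calculation (0.092 down to 0.066 for R² of 0.05 to 0.20) to every test at 0.10. Those figures fit only the pairwise priming-sequence comparisons. The overall sequence test has 2 df, and the adjuvant comparisons run at 0.0554 each.

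**Conclusion.** The mismatch between allocation and analysis is confirmed. Its consequence depends on whether centre, sex, age class and vaccination history predict the post-vaccination titre beyond the Day 1 titre. If they do, the planned analysis is conservative, to the extent set out above for R² up to 0.20 and close balance; if they do not, nothing is lost. For the 1.50 rule the practical effect is modest even at the top of the assumed range. The change is worth making because it costs little and bears on the plan's only adjuvant pass/fail criterion.

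**What to change.** If the unblinded Day 85 analysis has not been run, amend sections 6.2.3.1, 6.2.3.2 and 12.1. Next to the Day 1 log10 titre, add sex, age class (18-30 vs 31-39 years), influenza vaccination since 2014/2015 (yes/no) and centre. Pool sparse centres by a rule fixed beforehand, or fit centre as a random effect. Keep the present model as a sensitivity analysis and bring the Template 36 footnote into line.

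If that analysis has already been run, keep the present model as primary for the 1.50 rule and add the factor-adjusted model as a specified sensitivity analysis.

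The cost is one sentence in each of three sections and a changed model statement. Sex, age class and history take one df each. Centre, as a fixed effect, takes one fewer than the number of centres after pooling; the SAP does not give the number of centres. The 94.46% level stays as it is.
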